Detectable levels of marijuana in the drug screen are not exclusionary, if in the Investigator's documented opinion the subject does not meet DSM-V criteria¹³ for substance use disorder, and the positive test does not signal a clinical condition that would impact the safety of the subject or interpretation of the study results. Subject must agree to refrain from marijuana use during the study.

3. Allergies and Adverse Drug Reactions

- a) History of drug or other allergy which, in the opinion of the investigator, makes the subject unsuitable for participation in the study.

4. Sex and Reproductive Status

- a) WOCBP who are unwilling or unable to use required contraception. Refer to Section 16.6 Appendix 6 for Contraceptive and Barrier Guidance). Women who are pregnant or breastfeeding.
- b) Women with a positive pregnancy test at Screening Visit or prior to study drug administration

5. ECG and Laboratory Test Findings

- a) Any clinically significant abnormality identified on the medical or laboratory evaluation. A subject with a clinical abnormality or laboratory parameters outside the reference range may be included only if the Investigator considers the finding not clinically significant, that it will not introduce additional risk factors, will not interfere with the study procedures, and does not otherwise meet any expressly written exclusionary criterion within the protocol.

- b) Estimated glomerular filtration rate (eGFR) according to the re-expressed abbreviated (four-variable) Modification of Diet in Renal Disease (MDRD) Study equation < 30 ml/min/1.73m²
- c) Total bilirubin $> 1.5 \times$ ULN (For Gilbert's syndrome, direct bilirubin $>$ ULN is exclusionary).
- d) AST or ALT $> 2 \times$ ULN.
- e) Serum albumin < 2.8 g/dL
- f) Neutrophil count $\leq 1,000/\mu\text{L}$ (or equivalent)
- g) HbA1c $> 7.5\%$
- h) The subject has evidence of organ dysfunction or any clinically significant deviation from normal on physical examination, vital signs, 12-lead electrocardiogram (ECG), or clinical laboratory determinations beyond what is consistent with the target population. Abnormal ECG that in the investigator's opinion makes the subject unsuitable for a clinical trial.

6. Prohibited Medications and Devices

- a) Recognized migraine-preventive medication taken within 30 days prior the Screening Visit (see Section 16.2 Appendix 2). Note the following exceptions:

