 - i. Biologic migraine medication (such as CGRP antagonist monoclonal antibodies) taken within 6 months (24 weeks) prior to the Screening Visit
 - ii. Botulinum toxin injections (e.g., Botox®) used for the prevention of migraine taken within 3 months (12 weeks) prior to the Screening Visit
- b) Non-Narcotic Analgesics (e.g., nonsteroidal anti-inflammatory drugs [NSAIDs] or paracetamol [acetaminophen] taken ≥ 15 days per month during the 3 months (12 weeks) prior to the Screening Visit
- c) Cefaly™ or any other device for migraine prevention or treatment within 3 months (12 weeks) prior to the Screening Visit
- d) Ergotamine taken ≥ 10 days per month on a regular basis for ≥ 3 months (≥ 12 weeks) in the year prior to the Screening Visit
- e) Narcotic, such as opioid (e.g., morphine, codeine, oxycodone, hydrocodone) or barbiturate (e.g., butalbital), taken for ≥ 4 days per month during the 3 months (12 weeks) prior to the Screening Visit

- f) Permitted acute migraine medication taken ≥ 15 days per month for a non-headache indication during the 3 months (12 weeks) prior to the Screening Visit (see Section 5.5)
 - i. Low dose aspirin (e.g., up to 100 mg daily) for documented cardiovascular prophylaxis is allowed.

Note: See Section 5.7 and Section 16.3 Appendix 3 for further details related to prohibited medications and devices

7. Other Exclusion Criteria

- a) Non-compliance with or inability to complete eDiary during Observation Phase. Subjects with less than 24 completed eDiary reports during the first 28 days in the Observation Phase will not be considered for participation due to non-compliance with the eDiary.
- b) Exposure to non-biological investigational agents within 30 days prior to the Screening Visit
- c) Exposure to biological investigational agents (including monoclonal antibodies) within 6 months (24 weeks) prior to the Screening Visit
- d) Previous enrollment in any multiple dose BHV3000 (rimegepant) study, such as BHV3000-201, BHV3000-305, BHV3000-405, or BHV3000-406, regardless of the number of doses taken. Subjects may be considered for BHV3000-407 if the subject participated in any of the following single dose studies: BHV3000-301, BHV3000-302, BHV3000-303, but did not participate in any multiple dose rimegepant study. Note that subjects who were considered screen failures in a past BHV3000 study may be considered after discussion with the Sponsor and written approval is received.

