16.3. Appendix 3 – Prohibited and Restricted Concomitant Medications and Devices

Use of the following medications and devices is prohibited or restricted during the study (i.e., starting from the Screening Visit and through the Follow-up Week 2 Visit), unless otherwise specified.

- Use of the following recognized migraine-preventive medications within 30 days prior to the Screening Visit and throughout the study, unless otherwise specified:
 - All prophylactic treatments targeting the CGRP pathway
 - Oral small molecules (e.g., atogepant, non-study rimegepant, etc.)
 - Injectable monoclonal antibodies (e.g., eptinezumab, erenumab, fremanezumab, galcanezumab, etc.)- these particular medications must be discontinued at least **6 months** (24 weeks) prior to the Screening Visit and throughout the study
 - ACE inhibitors / Angiotensin receptor blockers: candesartan, lisinopril
 - Alpha-adrenergic agonists: clonidine, guanfacine
 - Antidepressants: amitriptyline, desvenlafaxine, duloxetine, milnacipran, nortriptyline, protriptyline, venlafaxine
 - Antiepileptics: gabapentin, topiramate, valproic acid (sodium valproate, divalproex sodium)
 - Beta-blockers: atenolol, bisoprolol, metoprolol, nadolol, nebivolol, pindolol, propranolol, timolol
 - Calcium channel blockers: flunarizine, lomerizine, nifedipine, nimodipine, verapamil
 - Onabotulinumtoxin A (Botox[®]) taken within **3 months** (12 weeks) prior to the Screening Visit and throughout the study
 - Serotonin antagonists: methysergide, oxetrone, pizotifen
 - Vitamins / Supplements: butterbur, feverfew, magnesium citrate (≥ 600 mg/day), riboflavin (Vitamin B2; ≥ 100 mg/day)
 - Other locally-approved, or otherwise recognized standard of care, medications used for the preventive treatment of migraine, unless otherwise specified
- Note: Stable use (consistent dosing frequency and strength at least 3 months [12 weeks] prior to the Screening Visit and afterward) of the above migraine preventive medications for non-headache indication is allowed, unless otherwise specified. The above medications are NOT permitted to be newly initiated at any time during the course of the study (e.g., Screening, DBT, or OLE Phases)

- All devices and/or invasive interventions used for the preventive treatment of migraine (e.g., nerve blocks, occipital nerve stimulators, transcranial magnetic stimulation, etc.) administered within 3-months(12 weeks) of the Screening Visit and throughout the study

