- Number of ROM medication categories with previous inadequate response discrepant between the RTSM system and nonstudy medication CRF data. ROM medication categories based on nonstudy medication CRF data are defined in Section 9.4.2. This is defined as any of the following subcategories:
  - RTSM value of “2” and CRF value  $\leq 1$ ,  $\geq 3$ , or missing
  - RTSM value of “3 to 4” and CRF value  $\leq 2$ ,  $\geq 5$ , or missing.

See Section 6.2.5.1.

- DB study drug dosing noncompliance, defined as any of the following subcategories (see Sections 6.2.6.2 and 9.5):
  - DB study drug taken but not randomized
  - DB tablet count compliance  $< 80\%$  from study drug start to later of last scheduled DBT Phase visit or DB study drug end/OL rimegepant start
  - $> 1$  DB tablet taken on any 1 day
  - Consecutive DB study drug dosing days
  - Incorrect DB study drug taken.
- OL rimegepant dosing noncompliance, defined as any of the following subcategories (see Sections 6.2.6.2 and 9.5):
  - OL rimegepant tablet count compliance  $< 80\%$  from OL rimegepant start to later of last scheduled OLE Phase visit or OL rimegepant end
  - $> 1$  OL rimegepant tablet taken on any 1 day
  - Consecutive OL rimegepant dosing days
  - OL rimegepant start on or before DB study drug end
  - OL rimegepant taken but DB study drug never taken.
- eDiary usage compliance  $< 80\%$  from study drug start to later of last scheduled DBT Phase visit or DB study drug end/OL rimegepant start (see Section 6.2.6.2)
- Prohibited nonstudy medications taken on or after informed consent (or otherwise specified), defined as any of the following subcategories:
  - Atypical antipsychotic, divalproex, valproic acid, or valproate #
  - Ergotamine
  - Lamotrigine
  - Recognized prophylactic migraine medication taken up to 30 days before informed consent or afterward #. Recognized prophylactic migraine medication is defined as prophylactic migraine medication with preferred name containing any preferred name listed in the latest version of the sponsor-provided file Recognized Migraine Prevention

Medications.xlsx or equivalent. Prophylactic migraine medication is defined in Section 6.2.6.3.

- Narcotic (barbiturate or opioid) #
- Select moderate or strong cytochrome P450 3A4 (CYP3A4) inducer #
- Select strong CYP3A4 inhibitor #.

Note that nonstudy medications with route of “topical” or “intraocular” are excluded.

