For the subcategories marked with “#”, preferred names are displayed alphabetically as additional subcategories. Medications taken up to  $X$  days before a reference date or afterward are defined as those with imputed medication start date or imputed end date  $\geq$  reference date –  $X$ . Refer to the Core SAP for additional details about prohibited nonstudy medications.

The RTSM randomization date is the reference date for “randomization”. If the RTSM randomization date is missing, then the study drug start date is used.

The protocol version to which subjects consented is determined from the Inclusion/Exclusion Criteria CRF.

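### SAP 9.1 counts every migraine preventive with one 30-day look-back, shorter than the protocol's washouts for biologics and botulinum toxin, and its valproate bullet does not match Appendix 3

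*SAP*

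**What the plan says.** **Protocol.** Exclusion 6a (section 5.3) begins with a general rule: "Recognized migraine-preventive medication taken within 30 days prior the Screening Visit". It then lists two classes as exceptions to the 30 days. The first is "Biologic migraine medication (such as CGRP antagonist monoclonal antibodies) taken within 6 months (24 weeks) prior to the Screening Visit". The second is botulinum toxin injections "used for the prevention of migraine taken within 3 months (12 weeks) prior to the Screening Visit". Appendix 3 (section 16.3) repeats both longer periods. Of the injectable antibodies it says that "these particular medications must be discontinued at least" 6 months (24 weeks) before Screening.

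**SAP.** Section 9.1 puts preventives in one subcategory of prohibited medication, "Recognized prophylactic migraine medication taken up to 30 days before informed consent or afterward". The date rule that follows is that medications taken up to X "days before a reference date or afterward are defined as those with imputed medication start date or imputed end date" on or after the reference date minus X. No other subcategory in section 9.1 covers biologics or botulinum toxin.

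**Valproate.** A separate bullet in SAP 9.1, "Atypical antipsychotic, divalproex, valproic acid, or valproate", applies to use on or after informed consent and has no condition on indication or stability. Protocol Appendix 3 lists valproic acid among the preventives and then notes that stable use "of the above migraine preventive medications for non-headache indication is allowed, unless otherwise specified".

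**The concern.** The relevant-deviations table and listing (SAP 6.2.4.1) are where a reader will check whether the randomized subjects respected the protocol's washouts. The table prints subcategories even when the count is zero, so a low figure looks like evidence of compliance. A look-back of 30 days cannot detect most of a 24-week or 12-week washout, so the figure would understate breaches for the two classes to which the protocol gave the longest periods. The valproate bullet can err in the other direction: a subject whose use Appendix 3 allows would be counted as a deviation. What is at stake is the accuracy of the deviation report.

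**Working it through.** The plan states no figure on this point, so there is nothing to reproduce. The check is a day count for the washouts and a comparison of texts for valproate.

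**Washouts: inputs**
- SAP look-back: 30 days before informed consent (SAP 9.1).
- Protocol washout W: biologics 24 × 7 = 168 days; botulinum toxin 12 × 7 = 84 days; other recognized preventives 30 days (protocol 5.3, exclusion 6a; Appendix 3).
- Reference dates: the SAP counts from consent and the protocol from Screening. Consent is obtained at the Screening Visit (protocol 4.3.1.1 and 7.2.1), so I take the two dates as equal.
- Assumption: the recorded end date is the date of the last dose, d days before consent.

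**Washouts: rule and result**
- The protocol is breached before consent when 1 ≤ d ≤ W.
- The SAP flags when (reference date − d) ≥ (reference date − 30), that is, when d ≤ 30. The start date adds nothing, because it cannot be later than the end date.
- Breached but not flagged: 31 ≤ d ≤ W, which is W − 30 days.
- Biologics: 168 − 30 = 138 days (days 31 to 168); 138/168 = 82%.
- Botulinum toxin: 84 − 30 = 54 days (days 31 to 84); 54/84 = 64%.
- Other recognized preventives: 30 − 30 = 0 days, so no gap.

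These percentages describe the length of the window. They would be percentages of breaches only if last doses were spread evenly over the washout, and the documents give no basis for that. Depending on when the last doses fell, the share of actual breaches missed could be anything from 0% (all in the final 30 days) to 100% (all earlier).

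**Valproate: the texts side by side**
- SAP 9.1 counts any use from consent onward.
- Protocol Appendix 3 allows stable use, from at least 12 weeks before Screening, for a non-headache indication, subject to contrary wording elsewhere. The current appendix has no separate valproate prohibition; atypical antipsychotics, which share the SAP bullet, have their own entry there without valproate.
- Protocol exclusion 6a refers to the Appendix 2 list, which includes valproate, and states no non-headache exception. The note closing that block of criteria sends the reader to Appendix 3 for detail.

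So a stable non-headache valproate user is counted by the SAP, allowed by Appendix 3, and not clearly placed by exclusion 6a. The SAP is also uneven between drugs. Other listed preventives are counted only if they meet the prophylactic definition in SAP 6.2.6.3, which requires entry on the previous-experience form or a prophylactic indication. Stable topiramate for another indication, recorded only on the Concomitant Medications form, would not be counted; valproate in the same position would be.

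**The case against.** The strongest reply is that SAP 9.1 was never a full audit of eligibility. It leaves out other exclusion criteria, such as HbA1c, bilirubin and AST/ALT, and the preventive bullet sits among subject-management deviations, not eligibility deviations. That is fair as to scope. But the bullet does reach back before consent, so it acts as a washout check, and elsewhere section 9.1 follows protocol limits closely, splitting the eGFR and BMI thresholds by protocol version. A check that is included should use the protocol's windows.

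A second reply is that SAP 9.1 defers to the Core SAP and to a sponsor file of drug names, neither of which was available. Either could add a filter, and that uncertainty stands. A list of names would not lengthen the explicit 30 days, however.

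A third is that breaches can be seen elsewhere. Protocol 5.11 requires significant eligibility departures to be documented. SAP 6.2.4.2 lists deviations reported as major, and SAP 6.2.5.4 and 6.2.6.3 tabulate or list previous and nonstudy medications. This also stands. A reader might infer that the report would show washout breaches as zero. The documents do not support that: breaches within 30 days are counted under SAP 9.1, and earlier ones may appear in those other outputs.

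A reader might also infer that non-study rimegepant recorded as acute treatment is a prohibited drug that slips through. Appendix 3 names it under prophylactic treatments, so the documents do not establish that acute use is the breach the bullet is meant to find.

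**Conclusion.** The point holds for deviation reporting. As written, SAP 9.1 omits from the relevant-deviations table and listing any biologic last taken 31 to 168 days before, and any botulinum toxin last taken 31 to 84 days before. The valproate bullet is a separate mismatch and does not come from the 30-day rule. This rests on consent and Screening falling on the same date, on end dates marking last doses, and on the unseen Core SAP not overriding the stated window. The number of subjects affected cannot be estimated from the documents, and exclusion 6a should keep it small.

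A reader might go further and infer bias in the primary endpoint, through a lowered Observation Phase baseline or a diluted contrast with placebo. The documents do not support this as a consequence of the SAP rule. No analysis set in SAP 4.1 removes a subject for these deviations, no per-protocol set is defined, and SAP 3.2 handles nonstudy prophylactic use by a treatment policy strategy. Correcting the rule leaves the primary estimate, its standard error and its p-value unchanged.

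**What to change.** In SAP 9.1, divide the preventive subcategory so that each look-back matches the protocol's own window, counted back from the Screening Visit:
- biologic preventives: 168 days;
- botulinum toxin for migraine prevention: 84 days;
- all other recognized preventives: 30 days;
- on-study use, in each case.

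Confirm that the sponsor's drug-name file contains the biologics and botulinum toxin, since a drug missing from it would not be flagged at all. Reconcile the valproate bullet with Appendix 3 and exclusion 6a. The sponsor should settle which reading is intended and make the three texts agree.

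The cost is a few lines of SAP text and programming. For medications actually taken, the previous-experience form already collects start and end dates, including those under its other migraine-preventive category (SAP 9.4.1). No new data, change of conduct or change to an efficacy analysis is needed. Counts for the two long-washout classes may rise slightly.

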## 9.2 eDiary Efficacy

### 9.2.1 Efficacy Parameters

On a given day, subjects use the eDiary to provide responses to the following efficacy parameters occurring yesterday:

- Headache (yes, no)
- If the response to headache is “yes”, then responses to the following pain features and associated symptoms are collected:
  - Lasts at least 30 minutes (yes, no)
  - Pain intensity (mild, moderate, severe)
  - Unilateral (yes, no)
  - Pulsating (yes, no)
  - Worsen or avoid physical activity (yes, no)
  - Nausea (yes, no)
  - Vomiting (yes, no)
  - Photophobia (yes, no)
  - Phonophobia (yes, no)
- Aura (yes, no)
- If the response to headache or aura is “yes”, then the responses to the following parameters about taking medications to treat headache or aura are collected:

- Triptan (yes, no)
- Ergotamine (yes, no)
- Lasmiditan (yes, no)
- Ubrogapant (yes, no)
- Other medication (yes, no).

These efficacy parameters are collected together as a set with the same eDiary finding date/time for a subject. It is expected that subjects have only 1 set of efficacy parameters collected on a given eDiary finding date. Handling of multiple sets on the same date are discussed in subsequent sections.

### **9.2.2 eDiary Efficacy Data Day**

A day of eDiary efficacy data is defined as any complete eDiary efficacy data date (see Section 7.1).

### **9.2.3 Acute Migraine Medication Day**

An acute migraine medication day is defined as either (1) or (2):

- 1) Acute migraine-specific medication day (see Section 9.2.4)
- 2) Migraine day (see Section 9.2.5) with a “yes” response to the question about taking other medications to treat headache or aura.

Thus, acute migraine medication days are a subset of migraine days (see Section 9.2.5). If there are multiple sets of efficacy parameters on the same finding date, then data from all sets are used cumulatively to assess acute migraine medication day status on that day, regardless of finding time. For example, if a subject has both “yes” and “no” responses to the question about taking triptan on that day, then the subject is considered to have taken triptan on that day.

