During the Observational Phase, DBT Phase and OLE Phase, any calendar day during which a subject takes a migraine-specific acute migraine medication (i.e., triptan, ergotamine, lasmiditan, or ubrogepant), the corresponding calendar day will be counted as an "acute migraine medication day" and an "acute migraine-specific medication day", regardless of the duration and pain features/associated symptoms.

Of note, the use of ergotamine is prohibited throughout the entire duration of the study. However, all dosing of acute migraine-specific medication (i.e., triptan, ergotamine, lasmiditan, and ubrogepant) must be reported within the eDiary(DBT) and the Concomitant Medication paper diary, to accurately inform the occurrence of a "migraine day".

In addition, any calendar day during which a subject takes an acute migraine medication (permitted [see Section [16.4 Appendix 4](#)] or non-permitted) for the reported purpose of treating a qualifying migraine headache (or aura), then the corresponding calendar day will be counted as an "acute migraine medication day".

All use of acute migraine medications (permitted or otherwise) for the purpose of treating a qualified migraine headache will be recorded from the Screening Visit to the Follow-up Week 2 visit on the Concomitant Medication paper diary.

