6.4. Efficacy Assessments

The eDiary will be used daily to record any acute migraine-specific medication dosing occurrences (i.e., triptan, ergotamine, lasmiditan, or ubrogepant), each migraine occurrence, related migraine pain features, and other associated symptoms during the Observation Phase and everyday during the DBT Phase.

Of note, the use of ergotamine is prohibited throughout the entire duration of the study. However, all dosing of acute migraine-specific medication (i.e., triptan, ergotamine,

lasmiditan, and ubrogepant) must be reported within the eDiary and the Concomitant Medication paper diary, to accurately inform the occurrence of a “migraine day”.

Efficacy assessments will be derived from eDiary data and will include the number of migraine days per month by headache pain intensity (total; moderate or severe), and number of acute migraine medication days (see Section 5.5) per month, by study period. A month is defined as 28 days, for the purpose of this protocol.

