### **Data Sources for Endpoints**

Migraine days, acute migraine-specific medication days, acute migraine medication days, headache days, MFIQ scores, and PGA – Migraine scores during the DBT Phase are derived from electronic diary (eDiary) data from the external source YPrime. Acute migraine-specific medications are triptans, ergotamine, lasmiditan, or ubrogepant. Acute migraine medications are acute migraine-specific medications and other protocol-allowed medications to treat headache (migraine or nonmigraine) or aura taken on a migraine day.

AEs are determined from AE CRFs.

Grade 3 to 4 laboratory test abnormalities are determined from laboratory test values graded using standardized criteria (see Section 6.4.2 for more details). Laboratory test results are from an external central laboratory and local laboratory test CRFs.

Endpoints based on other rating scale and questionnaires (i.e., C-SSRS, HIT-6, MIBS, MSQ, WPAI – Migraine, PGA – Migraine during the OLE Phase) are derived from their respective CRFs.

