#### **6.3.3.7      *Acute Migraine Medication Days per Month Over Time on DBT***

Acute migraine medication days per month are assessed analogously to acute migraine-specific medication days per month (see Section 6.3.2.2).

An acute migraine medication day is defined in Section 9.2.3.

Analyses are based on the migraine analysis set with eDiary efficacy data dates in the on-DBT efficacy analysis period.

The number of acute migraine medication days per month in the DBT Phase are prorated to 28 days.

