### **9.2.4 Acute Migraine-Specific Medication Day**

An acute migraine-specific medication day is defined as a day of eDiary efficacy data with a “yes” response to any of the 4 questions about taking triptan, ergotamine, lasmiditan, or ubrogapant to treat headache or aura.

Thus, acute migraine-specific medication days are a subset of acute migraine medication days and migraine days (see Sections 9.2.3 and 9.2.5, respectively). If there are multiple sets of efficacy parameters on the same finding date, then data from all sets are used cumulatively to assess acute migraine-specific medication day status on that day, regardless of finding time.

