### **9.2.5 Migraine Day**

A migraine day is defined as a day of eDiary efficacy data with either (1) or (2):

- 1) Qualified migraine headache, defined as meeting both criteria a and b:

- a. Headache lasting  $\geq 30$  minutes: “yes” response to the question about lasting  $\geq 30$  minutes
- b. Meeting  $\geq 1$  of the following criteria (i or ii):
  - i.  $\geq 2$  of the following pain features:
    - 1. Unilateral: “yes” response to the question about unilateral
    - 2. Pulsating: “yes” response to the question about pulsating
    - 3. Moderate or severe pain intensity
    - 4. Worsen or avoid physical activity: “yes” response to the question about worsen or avoid physical activity
  - ii.  $\geq 1$  of the following associated symptoms:
    - 1. Nausea: “yes” response to the question about nausea
    - 2. Vomiting: “yes” response to the question about vomiting
    - 3. Both photophobia and phonophobia: “yes” responses to the questions about photophobia and phonophobia

2) Acute migraine-specific medication day (see Section 9.2.4)

Migraine days are a subset of headache days (see Section 9.2.6).

If there are multiple sets of efficacy parameters on the same finding date, then data from all sets are used cumulatively to assess migraine day status on that day, regardless of finding time. Migraine pain intensity is set to the greatest pain intensity on that day.

A migraine day of total pain intensity is any migraine day, regardless of pain intensity.

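### SAP 9.2.3 leaves out days with aura only that are treated with non-specific medication, which Protocol 5.5 counts as acute migraine medication days

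*SAP*

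**What the plan says.** Protocol 5.5 has two routes to an acute migraine medication day. Any use of a triptan, ergotamine, lasmiditan or ubrogepant makes the day count. Any other acute migraine medication, permitted or not, makes it count if taken "for the reported purpose of treating a qualifying migraine headache (or aura), then the corresponding calendar day will be counted". Protocol 6.4 applies this to efficacy, listing the "number of acute migraine medication days (see Section 5.5) per month, by study period".

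SAP 9.2.3 keeps the first route. Its second requires a migraine day together with a yes "response to the question about taking other medications to treat headache or aura". It then draws the consequence: "Thus, acute migraine medication days are a subset of migraine days (see Section 9.2.5". SAP 3.2, under the data sources for endpoints, repeats the restriction: "other protocol-allowed medications to treat headache (migraine or nonmigraine) or aura taken on a migraine day". For the analysis, SAP 6.3.3.7 states: "An acute migraine medication day is defined in Section 9.2.3".

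Under SAP 9.2.5 a day becomes a migraine day in only two ways. One is a "Qualified migraine headache, defined as meeting both criteria a and b", which needs a headache of at least 30 minutes. The other is an acute migraine-specific medication day, which SAP 9.2.4 defines by a yes "response to any of the 4 questions about taking triptan, ergotamine, lasmiditan" or ubrogepant. Aura alone is not enough.

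**The concern.** The two documents define one endpoint differently. The trial enrols patients with or without aura, and Protocol 5.6 names aura-only events, so such days are foreseen. The SAP also treats like days unlike: an aura-only day counts if a triptan is taken and does not count if a simple analgesic is taken. The second day is not a headache day either, because the treated-headache criterion in SAP 9.2.6 requires a headache. It therefore appears in none of the eDiary day counts.

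The estimand text adds to the inconsistency. SAP 3.2 exempts this endpoint from the intercurrent event of other medication used for headache or aura, and Table 4 marks that event as not applicable. This makes sense if the endpoint itself captures such use, but on aura-only days it does not.

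At stake is whether exploratory objective 7 reports the quantity that the protocol describes.

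**Working it through.** The documents give no figure for this endpoint to reproduce. The sample size calculation concerns the primary endpoint and is not touched. The check is to apply both definitions to every diary pattern.

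**Patterns.** From SAP 9.2.1: headache (none, non-qualifying, qualifying), aura (yes, no), migraine-specific drug (yes, no) and other medication (yes, no). That gives 3 × 2 × 2 × 2 = 24. The medication questions are asked only if headache or aura is yes, which removes the 3 patterns with medication but neither symptom and leaves 21. Other medication on a day with a qualifying headache is taken to be for that headache or its aura.

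| Headache | Aura | Specific drug | Other medication | Protocol 5.5 | SAP 9.2.3 | Patterns |
|---|---|---|---|---|---|---|
| any | either | no | no | no | no | 6 |
| any | either | yes | either | yes | yes | 10 |
| qualifying | either | no | yes | yes | yes | 2 |
| non-qualifying | no | no | yes | no | no | 1 |
| **none** | **yes** | **no** | **yes** | **yes** | **no** | **1** |
| non-qualifying | yes | no | yes | only if taken for the aura | no | 1 |

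The total is 6 + 10 + 2 + 1 + 1 + 1 = 21. Nineteen patterns agree and one disagrees with certainty. One depends on purpose, which the eDiary does not record: it has a single other-medication item covering headache and aura together. In no pattern does the SAP count a day that the protocol leaves out.

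**Size for one subject.** Counts are prorated as 28 × (medication days) / (eDiary data days). With *k* omitted days among *D* data days in a month, the SAP value is lower by 28*k*/*D*. That equals *k* for a full diary (*D* = 28) and 2*k* at the evaluability minimum (*D* = 14). The documents give no information on *k*, and it may be 0.

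**Effect on the comparison.** Let *s*R and *s*P be the mean monthly shortfalls on rimegepant and placebo. On simple arm means, the SAP difference (rimegepant – placebo) equals the protocol difference minus (*s*R – *s*P). If each shortfall could lie anywhere from 0 to 0.5 days (an assumption for illustration only), the shift could lie anywhere from –0.5 to +0.5 days. Equal shortfalls give no shift.

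**Scope.** The affected outputs are exploratory objective 7 (SAP 6.3.3.7) and the Observation Phase summary in SAP 6.2.5.2. That summary does not enter the comparison, because the model has no baseline covariate. Migraine days and migraine-specific medication days do not use this definition, so the primary, key secondary and migraine-specific medication endpoints are unchanged. SAP 3.1.2.2 words other secondary objective 3 without the term migraine-specific, but SAP Table 3, SAP 6.3.2.2 and the protocol all make it the migraine-specific endpoint.

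**The case against.** The strongest defence is that the SAP was entitled to do this. Protocol section 9 lets the SAP modify the protocol outline and requires an amendment only for major changes to the primary endpoint. The SAP revision history records that version 3 modified this definition in both 3.2 and 9.2.3. The rule is stated in both places, and 9.2.3 spells out its consequence. It can be read as a prespecified choice to measure acute medication on migraine days, for an exploratory endpoint with unadjusted, descriptive p-values. This stands as far as it goes: the departure is permitted and disclosed. But no reason is given, the current protocol keeps aura as a trigger, and Table 4 fits the protocol's version better.

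One could also argue that the protocol's bracketed aura means only aura accompanying a qualifying headache. The words would then add nothing, since such a day already counts.

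Three stronger readings are tempting and not supported:

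- *Every treated aura-only day is scored as medication-free.* Days treated with a triptan, ergotamine, lasmiditan or ubrogepant count in both documents.
- *The SAP rule exaggerates the benefit of rimegepant.* That would follow if treatment turned migraine days into aura-only days still treated with an analgesic. If treatment instead reduced aura-only days, the rule would understate the benefit. The documents support neither.
- *The protocol definition can be programmed exactly.* It cannot be on days with aura plus a non-qualifying headache, because purpose is not recorded.

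**Conclusion.** The inconsistency is real and narrow. For one diary pattern with certainty, and a second depending on purpose, SAP 9.2.3 and 3.2 omit days that Protocol 5.5 counts. Relative to the protocol definition, the SAP count can only be equal or lower. A percentage undercount could be quoted only by assuming both a rate of such days and a typical monthly medication count, and the documents give neither. The shortfall and its effect on the treatment difference are therefore unknown and may be zero. The conclusion rests on reading aura in Protocol 5.5 as a trigger in its own right and on the eDiary structure in SAP 9.2.1. It is a minor point: an unexplained departure on one exploratory endpoint, not a prohibited one, and worth correcting because the correction is small.

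**What to change.** Add a third criterion to SAP 9.2.3: *a day of eDiary efficacy data with headache = no, aura = yes and other medication = yes*. Limiting it to days without headache avoids counting days on which the medication may have been for a non-qualifying headache. State separately how days with aura plus a non-qualifying headache and other medication are handled, since the eDiary cannot show which was treated.

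Replace the sentence in 9.2.3 that makes these days a subset of migraine days. The corresponding statement in 9.2.4 concerns migraine-specific drugs, remains true and can stay.

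In SAP 3.2, reword to *other medications taken on a migraine day to treat headache or aura, or taken to treat aura on a day without headache*. Simply deleting the migraine-day condition there would let in medication for non-migraine headache, which Protocol 5.5 does not count.

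If the restriction is intended, amend Protocol 5.5 to match the SAP and give the reason.

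The cost of the SAP route is a wording change and one programming condition on data already collected. Either route is best settled before the primary completion database lock, up to which SAP 2.3 keeps the study blinded.
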